1.1 Study Rationale

This drug utilization study (DUS) is being conducted as part of the BMS/AZ Dapagliflozin Risk Management Plan. Per regulatory request, this study is being conducted to describe the patients using dapagliflozin in usual clinical practice in Europe, specifically the countries reporting to our data source: Belgium, France, Germany, Italy, Spain and United Kingdom. The selection of the Cegedim Strategic Data was made because it includes data across 6 different European countries. However, an analysis of dapagliflozin patients not only required a European approval but it also requires reimbursement at the country level. As of November 2013, reimbursement was achieved in the United Kingdom and was not achieved in Belgium. In Germany, dapagliflozin was only reimbursed for 2013. Reimbursement in Italy and Spain has yet to be determined and in France, dapagliflozin is not yet reimbursed but it is expected that, should we be reimbursed, it would be only for specialist use. Since the Cegedim database includes only general practitioners, we would not expect to see any dapagliflozin users from France. Therefore, at this time, sensitivity analyses around missing data will be limited to discussions of the UK data. As this study will be on-going through 2017, country reimbursement status may change potentially resulting in more useable data from the Cegedim database.

1.2 Research Question

Research question 1: What are the baseline characteristics of the patients prescribed dapagliflozin in Europe?

Research question 2: What proportion of patients prescribed dapagliflozin have baseline moderate to severe renal impairment?

Research question 3: What proportion of patients prescribed dapagliflozin are 75 years of age or older at the time of the index prescription?

Research question 4: What proportion of patients prescribed dapagliflozin are also users of loop diuretics or pioglitazone during the baseline period and the available follow-up period?

Research Question 5: What proportion of patients prescribed dapagliflozin does not have a diagnosis of Type II Diabetes during the baseline period or on the index date?

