Study Population: All patients identified in the database(s) who newly received at least one dapagliflozin prescription during the study period. Dapagliflozin use will be representative of the uptake of dapagliflozin in the respective countries.

Data Collection Methods: Cegedim Strategic Data (CSD) Longitudinal Patient Databases (LPDs) come directly from physicians' EMR. Participating physicians use CSD-provided software to record their daily patient interactions and data are transmitted regularly to the Cegedim coordinating center where they are cleaned and de-identified.

Data Sources: CSD's LPDs include data from 5.8 million active patients. Over 4,000 general practitioners (GPs) in six European countries (Belgium, France, Germany, Italy, Spain and United Kingdom) are part of the LPD panels.

Patient metrics in the LPDs include Demographics (Year of birth, gender, registration dates), Medical History (Event dates, diagnosis, symptoms, risk factors, co-morbidities, referrals), Prescription (Rx dates, indication, therapeutic class, molecule, brand, dosage, posology, duration), Clinical Data (Height, weight, BP, life habits) and laboratory data.

Exposures: A patient will be identified as newly exposed when he/she has at least one dapagliflozin prescription recorded in the study database(s).

Outcomes: Outcomes include but are not limited to:

- Patient demographics: age, sex, country,
- Baseline history of type 2 diabetes,
- Baseline history of moderate or severe renal impairment,
- Concomitant medications at baseline and during dapagliflozin use.

Follow-up: Follow-up will begin on the date a patient is first prescribed dapagliflozin, which will represent the beginning of follow-up (i.e., "index date"). Follow-up will continue until the end of study or discontinuation of dapagliflozin (i.e., the final day of the days' supply for the last prescription for dapagliflozin). Follow-up will only be used to determine combination use with loop diuretics or pioglitazone. The baseline period is defined as the 12 months in the database preceding the index date.

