2 OBJECTIVES

2.1 Primary Objectives

To describe the characteristics of European patients newly prescribed dapagliflozin by age, sex, dapagliflozin dose, country, selected co-morbidities, and selected concomitant medications.

The proposed drug utilization study will specifically describe dapagliflozin use among all new dapagliflozin users including dapagliflozin users in the following subgroups (separate analysis for each subgroup):

- patients > 75 years-old,
- combination use with loop diuretics or pioglitazone,
- patients with a known history of moderate or severe renal impairment and in kidney failure,
- patients not reported to have T2DM.

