3.1 Overview of Study Design

This is a cross-sectional observational single-arm cohort study with descriptive data analyses among patients receiving dapagliflozin within the Cegedim Strategic Data (CSD) Longitudinal Databases (LPDs) electronic medical records (EMRs) in Europe. The assessment of combination use with loop diuretics or pioglitazone will incorporate longitudinal follow-up (See Figure 3.1-1). The study will describe the utilization pattern of dapagliflozin during the first three and a half years after marketing authorization and launch in Europe, specifically the countries reporting to this data source: Belgium, France, Germany, Italy, Spain and United Kingdom. This analysis will be repeated at 18, 30 and 42 months from the launch of dapagliflozin (T0, estimated as January 1, 2013).

The "prescription index date" for each patient included in the study will be defined as the date a patient is first prescribed dapagliflozin.

Follow-up of Subjects

The follow-up period will be used to identify concomitant use of dapagliflozin with loop diuretics or pioglitazone. Follow-up will begin on the date a patient is prescribed dapagliflozin, which will represent the beginning of follow-up (i.e., "index date"). Follow-up will continue until the discontinuation of dapagliflozin (i.e., the final day of the days' supply for the last prescription for dapagliflozin). Once a new user of dapagliflozin discontinues his/her treatment at any time (could also include an interruption in treatment), he/she will not be identified for future analyses.

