3.3.1 Content of the Cegedim LPDs

Data are entered during usual patient care and submitted daily to the Cegedim coordinating center, cleaned and de-identified and then made available in the LPDs for research no later than one month after submission. The following anonymized patient data collected from GPs' practice will be extracted from the databases:

- Demographics (Year of birth, gender, registration dates),
- Medical History (Event dates, diagnosis, symptoms, risk factors, co-morbidities, referrals,
- Treatments (indication, molecule/brand, dosage, posology, date and length of prescription),
- Clinical Data (Height, weight, BP, life habits),
- Clinical laboratory tests, X-ray and other investigations (not available in Germany).

The median follow-up duration of a patient in the data base is 27 months in Germany, 36 months in France, 44 months in Spain, 46 months in Belgium, 112 months in Italy and 117 months in UK.

Patient data collected by Cegedim in each country participating in the LPD varies to some extent to accommodate local needs. However, all countries collect data on medical co-morbidities and outcomes, prescriptions, demographics, and physician characteristics. Key metrics of the GPs' LPDs are provided for each country in Appendix 2 (2012 data).

In the LPDs, diagnoses of clinical events are recorded as diagnostic codes (*e.g.* ICD-9, READ). These codes from the different participating countries will be harmonized based on pre-specified algorithms developed prior to the analysis and listed in the statistical analytic plan. Table 3.3.1-1 summarizes the coding conventions for each of the databases.

Table 3.3.1-1: Data Coding Conventions in the Different Countries

	Belgium	France	UK	Italy	Germany	Spain
Drug code dictionary	Association Pharmacologique Belge	Claude Bernard	Multilex	Farmadati	Abdata	Vademecum
Therapy classification	European Pharmaceutical Marketing Research Association (EphMRA)		British National Formulary (BNF)	ATC	ATC	ATC
Disease classification	Cegedim prop thesaurus (mapped	-	Read Codes	ICD-9	ICD-10	CIAP mapped to ICD-9

ATC = Anatomic, Therapeutic, Chemical

ICD = International Classification of Disease

CIAP = International Classification of Primary Care

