3.4.1 Outcomes/Endpoint Variables

Table 3.4.1-1 includes the characteristics and definitions of how dapagliflozin users will be categorized and described.

Table 3.4.1-1: Categorization of Dapagliflozin Users

Characteristic	Definition
Patient Demographics, at initiation of dapagliflozin use:	
Age categories	< 45, 45-59, 60-74, >= 75
Sex	Male or Female
Country	Belgium, France, Germany, Italy, Spain, United Kingdom
Concomitant medications before, at initiation of and	Loop diuretics (ATC code C03Cx)
during dapagliflozin use 1	Pioglitazone (Actos, Glustin) (ATC code A10BG),
	Biguanides (ATC Code A10BA)
	Sulfonamide derivates (ATC code A10BB and A10BC)
	Dipeptidyl peptidase 4 inhibitors (DDP4) (ATC code A10BH)
	Glucagon-like peptide 1 (GLP-1, exenatide, liraglutide, ATC code A10BX),
	Alpha glucosidase inhibitors (ATC code A10BF).
	Insulin (ATC code A10A)
Concomitant co-morbidities, at initiation of dapagliflozin use:	
Baseline history of moderate renal impairment	CrCl or eGFR ² value between 30-60 within 12 months prior to the dapagliflozin dispensing
Baseline history of severe renal impairment	CrCl or eGFR value < 30 within 12 months prior to the dapagliflozin dispensing
Baseline history of renal failure	Diagnosis codes for end stage renal disease or dialysis (see Appendix 3)
Congestive heart failure	Diagnosis codes for congestive heart failure (see Appendix 3)
Hypertension	Diagnosis codes for hypertension (see Appendix 3)
Type 2 Diabetes Mellitus, at initiation of dapagliflozin use:	Diagnostic code for T2DM within 12 months prior to the dapagliflozin dispensing (see Appendix 3) OR
	Prescription for an antiglycemic medication within 12 months prior to the dapagliflozin dispensing

Table 3.4.1-1: Categorization of Dapagliflozin Users

Characteristic	Definition
Dapagliflozin Dose, at initiation of dapagliflozin	10 mg
use:	5 mg
Off-Label Use	Patients meeting one of the following criteria:
	 17 years old or younger on index date
	• 75 years of age or older on index date
	 No diagnostic codes for Type 2 Diabetes Mellitus, at or before the initiation of dapagliflozin use (see definition above)
	• Baseline history of moderate renal impairment (see definition above)
	• Baseline history of severe renal impairment (see definition above)
	• Baseline history of renal failure (see definition above)

^[1] Pioglitazone sales are suspended in France and Germany

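### Combination use with loop diuretics or pioglitazone is not fixed: baseline and on-treatment use are joined without saying whether they are pooled, both required or reported separately

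*Protocol*

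**What the plan says.** The primary objective (Protocol, section 2.1) names "combination use with loop diuretics or pioglitazone" as one of four subgroups, each with its own analysis. Four places bear on how it is measured.

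- Section 1.2, research question 4: the proportion of patients who "are also users of loop diuretics or pioglitazone during the baseline period and the available follow-up period".
- Synopsis, Follow-up: "The baseline period is defined as the 12 months in the database preceding the index date".
- Synopsis, Outcomes: "Concomitant medications at baseline and during dapagliflozin use". The matching row of Table 3.4.1-1 (section 3.4.1) begins "Concomitant medications before, at initiation of and" and continues with use during dapagliflozin.
- Section 3.1: "The follow-up period will be used to identify concomitant use of dapagliflozin with loop diuretics or pioglitazone". The same section says: "The assessment of combination use with loop diuretics or pioglitazone will incorporate longitudinal follow-up".

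Follow-up starts on the index date and ends, at the latest, on the last day supplied by the final dapagliflozin prescription. The Synopsis adds that follow-up serves only to determine combination use.

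**The concern.** Combination use means that two drugs are taken over the same time. A new user has no recorded dapagliflozin in the 12 months before index, so a prescription in that window cannot by itself show co-exposure. Research question 4, the Synopsis outcome and the table row all bring that window in, and two of them label it concomitant. Section 3.1 instead points to the period on dapagliflozin. No section requires overlapping supply or says what happens to a patient whose other drug ended at or before index.

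Pioglitazone and dapagliflozin both lower glucose, so replacing one with the other is a plausible reason to start dapagliflozin. Counting that patient would report moving off a drug as combining it. A loop diuretic stopped before index raises the same classification problem without the switching motive.

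The study was requested by a regulator, and this is one of the four uses it must specifically describe. It is also the only reason the study has a follow-up period. A subgroup with its own analysis needs one rule for who belongs to it, and the protocol gives none.

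**Working it through.** The protocol states no figure for combination use, so there is nothing to reproduce. The check sets out the readings that the text allows and then illustrates their effect.

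**Step 1. Three readings of research question 4, applied to three kinds of patient**

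| Patient | Used while on dapagliflozin? | (a) Use in either period | (b) Use in both periods | (c) Periods reported separately |
|---|---|---|---|---|
| Used the drug in baseline, stopped by index | No | Counted (wrong) | Not counted | Baseline line only |
| Used it in baseline and continued | Yes | Counted | Counted | Both lines |
| First started it during dapagliflozin | Yes | Counted | Not counted (wrong) | Follow-up line only |

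Readings (a) and (b) each misplace one group, in opposite directions. Reading (c) misplaces nobody in the tabulation, but it does not say which line defines the subgroup in section 2.1.

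**Step 2. Illustration**

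All inputs are assumptions; none is in the protocol. They apply to a single drug, and those who stop are taken not to restart.

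- b = 10% of initiators have a baseline prescription.
- s = share of those who stop at or before index: 30%, 50% or 70%.
- n = 3% of the remaining 90% start the drug during dapagliflozin, so n(1 − b) = 0.03 × 90% = 2.7%.

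Formulas:

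- On-treatment use = b(1 − s) + n(1 − b)
- Either period = b + n(1 − b) = 10% + 2.7% = 12.7% for every s
- Both periods = b(1 − s)

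| s | On-treatment use | Either | Either / on-treatment | Both | Both / on-treatment |
|---|---|---|---|---|---|
| 30% | 7.0 + 2.7 = 9.7% | 12.7% | 1.3 | 7.0% | 0.72 |
| 50% | 5.0 + 2.7 = 7.7% | 12.7% | 1.6 | 5.0% | 0.65 |
| 70% | 3.0 + 2.7 = 5.7% | 12.7% | 2.2 | 3.0% | 0.53 |

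Pooling is too high by b × s, here 3, 5 or 7 percentage points. Requiring both is too low by n(1 − b), here 2.7 points at every s. The directions follow from the definitions; the sizes follow only from the assumed inputs.

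**Step 3. Are the data there for a better rule?**

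Section 3.3.1 lists "Treatments (indication, molecule/brand, dosage, posology, date and length of prescription" among the extracted items, and section 3.1 already uses days' supply to end dapagliflozin follow-up. Overlap can therefore be computed from data already planned.

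**The case against.** A reader might infer that the protocol counts patients who switched from pioglitazone as combination users. The documents do not support that as a statement of fact. No section says that baseline use alone is enough. A literal reading of the conjunction in research question 4 requires both periods and leaves such a patient out. Section 3.1 ties concomitant use to follow-up, which is by construction a window on dapagliflozin, so the follow-up component can show whether the combination occurs in practice.

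The lists in the Synopsis and in Table 3.4.1-1 can also be read as time points to tabulate, which is natural in a descriptive study. A patient who switched would then appear, correctly, only under earlier use. The 12-month look-back has legitimate purposes too: describing baseline, and finding supply that runs across the index date.

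It can further be said that overlap rules belong in the SAP, which is not at hand. The details do: the algorithm and the tolerance. However, section 4.1 has the SAP elaborate on the protocol and sends major modifications to an amendment. A SAP would have to choose between research question 4 and section 3.1, or among readings that give different proportions.

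What stands of the objection is that the defect is an unsettled definition rather than a stated miscount, that one reading is benign, and that the size is unknown. What does not stand is that the benign reading settles the matter, since the subgroup still lacks a membership rule and earlier use is still labelled concomitant.

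**Conclusion.** The concern holds in this form: the protocol fixes combination use badly. Its sections point to different windows and do not say whether those windows are pooled, both required or reported separately. Two of the three readings give a wrong proportion for a primary, regulator-requested subgroup, one too high and one too low.

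No size can be derived from the protocol. The ratios of 1.3 to 2.2 for pooling and 0.53 to 0.72 for requiring both hold only under the assumed rates and the corresponding reading, and should not be quoted as an expected error. The pioglitazone part mainly concerns Belgium, Italy, Spain and the United Kingdom, because a note to Table 3.4.1-1 says sales are suspended in France and Germany. The loop-diuretic part is not limited in that way. The change should be made before the first extraction.

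**What to change.** Reconcile the Synopsis (Outcomes and Follow-up), research question 4, section 3.1 and Table 3.4.1-1 on one definition.

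- Define research question 4 and the combination-use subgroup by use on or after the index date while on dapagliflozin. This means either a loop diuretic or pioglitazone prescription issued during follow-up, or supply that overlaps dapagliflozin supply by more than a minimum stated in advance. The minimum matters: a one-day rule would still count a patient who switches with leftover tablets.
- Report each drug separately in three exclusive groups: baseline use only, use continuing across index, and new start during dapagliflozin. Combination use is the sum of the last two.
- Label use before index as prior use, for these two drugs and for the other glucose-lowering drugs in the same table row.

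The cost is a wording change and some programming on data already extracted. The downside is that overlap depends on the recorded prescription length, so a short sensitivity analysis should vary the overlap threshold.

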2 OBJECTIVES

2.1 Primary Objectives

To describe the characteristics of European patients newly prescribed dapagliflozin by age, sex, dapagliflozin dose, country, selected co-morbidities, and selected concomitant medications.

The proposed drug utilization study will specifically describe dapagliflozin use among all new dapagliflozin users including dapagliflozin users in the following subgroups (separate analysis for each subgroup):

- patients > 75 years-old,
- combination use with loop diuretics or pioglitazone,
- patients with a known history of moderate or severe renal impairment and in kidney failure,
- patients not reported to have T2DM.

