- Elderly (≥ 65 years): In general, no dosage adjustment is recommended based on age. Renal function and risk of volume depletion should be taken into account. Due to the limited therapeutic experience in patients 75 years and older, initiation of dapagliflozin therapy is not recommended.
- Patients at risk for hypotension due to effect of dapagliflozin on diuresis and blood pressure: Caution should be exercised in patients for whom a dapagliflozin-induced drop in blood pressure could pose a risk, such as patients with known cardiovascular disease, patients on anti-hypertensive therapy with a history of hypotension or elderly patients. For patients receiving dapagliflozin, in case of intercurrent conditions that may lead to volume depletion,

careful monitoring of volume status (e.g. physical examination, blood pressure measurements, and laboratory tests including haematocrit) and electrolytes is recommended. Temporary interruption of treatment with dapagliflozin is recommended for patients who develop volume depletion until the depletion is corrected.

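### The elderly subgroup for separate analysis is set at > 75 years in the objectives, but at 75 or older in research question 3, Table 3.4.1-1 and the label text

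*Protocol*

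**What the plan says.** Section 2.1 of the protocol states the only objective; sections 2.2 and 2.3 mark secondary and exploratory objectives as not applicable. It promises to describe use among all new users, including "dapagliflozin users in the following subgroups (separate analysis for each subgroup". The first subgroup listed is "patients > 75 years-old", and the synopsis objective has the same entry. Section 4.1.1.2 also speaks of patients older than 75, as one example of people who may be prescribed the drug by specialists.

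Elsewhere the boundary includes age 75:

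- Research question 3 (section 1.2): "What proportion of patients prescribed dapagliflozin are 75 years of age or older at the time of the index prescription".
- Age categories (Table 3.4.1-1, section 3.4.1): "< 45, 45-59, 60-74, >= 75".
- Off-label rule (same table): "75 years of age or older on index date".
- Label text in the introduction: "Due to the limited therapeutic experience in patients 75 years and older, initiation of dapagliflozin therapy is not recommended".

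No section says that the two cut-offs are meant to differ, or which one governs the subgroup analysis.

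**The concern.** A programmer working from section 2.1 would build a group aged 76 and over. One working from Table 3.4.1-1 would build a group aged 75 and over. Both would be following the protocol. If both were followed in one report, its age table and its elderly subgroup tables would rest on different patients under nearly the same label. A reader comparing them would find denominators that do not agree and no explanation for the gap.

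The analysis is run at 18, 30 and 42 months (section 3.1) and shared with the CHMP (section 4.3), so the mismatch could appear three times. The age year left out of the subgroup is also the first one covered by the label text that the protocol reproduces.

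**Working it through.** There is no stated figure to reproduce. The check compares every statement of the elderly cut-off and follows patients near the boundary through each one.

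**Cut-offs as written**

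| Place in the protocol | Cut-off | Use |
|---|---|---|
| Synopsis, objective | > 75 | named subgroup |
| Section 2.1 | > 75 | subgroup with separate analysis |
| Section 4.1.1.2 | older than 75 | example in a parenthesis |
| Introduction, label text | 75 and older | background |
| Section 1.2, research question 3 | 75 or older | proportion to be reported |
| Table 3.4.1-1, age categories | >= 75 | age table |
| Table 3.4.1-1, off-label use | 75 or older | off-label count |

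**Patients near the boundary, age in completed years at index**

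| Age | Research question 3 | Age category | Off-label by age | Section 2.1 subgroup |
|---|---|---|---|---|
| 74 | no | 60-74 | no | out |
| 75 | yes | >= 75 | yes | **out** |
| 76 | yes | >= 75 | yes | in |

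Only age 75 is treated in two ways. Write N(>= 75) for the count in the top age category, N(> 75) for the section 2.1 subgroup and n(75) for those aged exactly 75. Then

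N(>= 75) − N(> 75) = n(75).

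The subgroup denominator therefore falls short of the >= 75 row by n(75), and the two agree only if no initiator is aged 75.

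**Size.** The protocol gives no age distribution for dapagliflozin users or for the type 2 diabetes patients in the databases. Table 4.2-1 forecasts users by country and year only. So n(75) cannot be derived.

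**What is not touched.** Research question 3 and Table 3.4.1-1 agree with each other, and section 4.1.1 points to that table for the characteristics to be described. The category below the top one ends at 74, so a 75-year-old can only fall in >= 75. The headline proportion and the off-label count are therefore consistently defined.

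**The case against.** The strongest reply is that the operative definitions are already right. Table 3.4.1-1 uses 75 or older twice, and research question 3 uses it for the proportion. No age exclusion, test or sample size depends on the cut-off. The subgroup could be re-tabulated from the same extract at any time. All of this stands, and it makes the point minor. It does not remove the conflict, because section 2.1 promises a separate analysis of a group defined differently. An SAP that adopted either cut-off would contradict one part of the protocol.

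The wording in section 4.1.1.2 adds little weight: it is an example in a parenthesis and defines no analysis population.

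A reader might infer four stronger things that the protocol does not support.

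- *That the 75-year-olds are lost from the study.* They stay in the >= 75 category, the off-label count and the research question 3 proportion.
- *That a question set by the regulator is answered on the wrong patients.* Section 1.1 says the study is done at regulatory request to describe users in usual practice. It does not itemise the request, and the four bullets in section 2.1 are subgroups.
- *That a definite share of the elderly group is missing.* If user numbers are assumed to fall by a constant ratio q per year of age, the share aged exactly 75 is 1 − q. That only returns the assumed ratio.
- *That the data make the matter worse.* The listed demographics hold year of birth ("Demographics (Year of birth, gender, registration dates"). With age taken as index year minus birth year, > 75 keeps the 75-year-olds whose birthday is still to come. What it drops is a mix of 74- and 75-year-olds, not all 75-year-olds. Reporting a bound without the boundary birth year would reproduce the > 75 set itself. How age is derived from birth year is in any case commonly left to the SAP.

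**Conclusion.** The inconsistency is real and unreconciled, and it is minor. The separately described subgroup in section 2.1 and the synopsis starts one year of age later than research question 3, the age categories, the off-label rule and the label text. If followed as written, its denominator is smaller than the >= 75 row by the number of initiators aged 75. That number cannot be obtained from the protocol. The research question 3 proportion is not affected.

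The conclusion assumes that age is read in completed years, as the categories 60-74 and >= 75 suggest. It concerns the definition of a reporting subgroup and passes no judgement on the clinical advice in the label.

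**What to change.** Change the elderly subgroup to >= 75 years in the synopsis objective and in section 2.1, and align the example wording in section 4.1.1.2. The objectives then match research question 3 and Table 3.4.1-1, and the subgroup tables share a denominator with the >= 75 row.

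The cost is three wording edits, with no change to data extraction, sample size or methods. They are best made before the SAP is finalised, which section 4.1 places ahead of the first data extraction.
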